
# Emergency Medicine Prospective Protocol

trajectory types in 100% of replications, and the mean trajectories in those four groups were characterized correctly.

**Exploratory Aim:** Aligning with the NIH guidance on health economics research, we plan a cost analysis of the intervention to inform wider dissemination and implementation in settings outside of the ED. Unmeasured time costs for staff or for participants can be a key barrier to the implementation and long-term viability of a new intervention since preventive and screening recommendations can compete for implementation time from staff. We will address this potential barrier by measuring all relevant costs associated with the study interventions through primary data collection. We will measure the total costs of the intervention from participant and health system perspectives by gathering estimates of intervention resource requirements, including personnel costs, implementation time, participant time, and material costs. Resource costs will include intervention development, training, and implementation. All costs will be adjusted to US 2017 dollars using the Gross Domestic Product Price Index. Control costs will be adjusted to reflect the proportion of time study participants spend on the app. We will calculate costs of the intervention per child. Net costs (savings) will be calculated by subtracting mean costs per participant in the control condition from mean costs per participant who receive the basic TCBD and the enhanced TCBD interventions. Given typical skewness, we will report means, medians, standard errors, minimum, maximum, and quantiles to provide information on cost measures. Tests will be employed to assess distributions of cost measures and identify appropriate methods for generating confidence intervals, such as non-parametric bootstrapping. We will also estimate cost-effectiveness as measured by dollars per caregiver using a size-appropriate CRS and using the CRS correctly. Economic data will provide key information about the relative costs and benefits associated with the intervention, inform scalability, and help prioritize future implementation strategies in EDs and other settings that serve young children (e.g., doctor's offices, schools).

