# Emergency Medicine Prospective Protocol

to another ED. Childhood survivors of MCVs can experience lifelong sequelae, including mobility impairments, irreversible brain or spinal cord injuries, and post-traumatic stress disorder.

Universal strategies to promote child passenger safety provide recommendations for the population as a whole and are disseminated in national guidelines, state laws, and public education campaigns. These strategies have reached many caregivers but **current recommendations are not adopted for all child passengers.** Precision prevention strategies, targeted to those who have not responded to universal strategies, are urgently needed to reduce unintentional injuries from MVCs. Suboptimal child restraint system (CRS) use is lowest for infants, with about 10% prematurely using a forward-facing car seat with a harness or booster seat. Suboptimal CRS use increases considerably after a child's first birthday; roughly 30% of toddlers use a booster seat or seat belt alone and >50% of elementary school age children use a seat belt alone when they would benefit from a more protective restraint. The greatest risk for injury is among children who travel unrestrained. This is permitted by caregivers in increasing proportions as children progress from toddlers (5%) to teens (15%). Proportions of fatally injured unrestrained children increase from 27% among <4 year olds to 45% for 8-12 year olds.

Prior child passenger safety research has generally encouraged use of car seats or booster seats for children in traditional age categories. We propose to move beyond one-size-fits-all age-based approaches with an innovative precision prevention intervention that: 1) *targets caregivers with suboptimal child passenger safety behaviors*; 2) *integrates child size, anticipated growth trajectory, and current CRS into personalized recommendations for correct use of a size-appropriate restraint*; 3) *tailors messages on caregiver race/ethnicity and Self-Determination Theory constructs (autonomy, relatedness, competence)*; and 4) has a second level of *increased intensity* to address caregivers who do not change their child passenger safety behavior by Month 6 of the study.

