## ***3.2 Allocation to Interventional Group***

After completing the baseline survey, all caregivers will be randomized into one of two groups: 1) TCBD intervention group, or 2) control group. Computerized, block randomization (block sizes from four to eight) will be applied to assign eligible caregivers to the TCBD intervention or control group in a 3:1 ratio. Blocks will be stratified by age groups related to child passenger safety recommendations (<2 years – rear-facing CRS, 2-4 years – forward-facing CRS, 5-10 years – booster seat) and the child passenger safety behavior that led to eligibility for study (not using the recommended restraint currently or planning a premature transition in the coming 6 months).

After the 6-month follow-up assessment, caregivers in the intervention group only who continue suboptimal CRS use will be re-randomized by computer in a 1:1 ratio to receive either the basic or enhanced intervention. The enhanced TCBD will include one additional motivational interviewing (MI) session by phone in Month 7/8 and one to two additional tailored text messages in Months 7-12 (total of 7 tailored tips during these months compared to 4 tailored tips for those in the basic TCBD). The extra text messages will be sent to those in the enhanced TCBD group until size-appropriate restraint use is observed. Caregivers receiving enhanced TCBD will be encouraged to obtain a free seat check with a certified child passenger safety technician (CPST) in the community. The primary outcomes (size-appropriate CRS use and CPaSS) will be assessed in-person at Months 6 and 12. The secondary outcome, the CPaSS trajectory, is a measure of correct and consistent restraint use in response to the intervention and will be assessed by scoring photographs submitted by caregivers (Months 1-5; 7-11).

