## **3.3 Study Measures**

Over the course of this study, participants will complete the following surveys: screen, baseline, 6- and 12-month survey. At the 6-month follow-up, the participants will also complete a brief health literacy assessment called the Newest Vital Sign.

The selected measures for the surveys are reliable, valid, and have been pilot tested in the study population. Measures will be assessed at screening, baseline and re-assessed at the 6- and 12-month follow-up visits. Assessments will be self-administered or RC facilitated on a study iPad in the ED and at in-person follow-up assessments (Months 6 and 12). Skip patterns will reduce administration time. Our team has found baseline assessment lasting 20 minutes to be feasible and acceptable to caregivers in the ED setting during pilot testing.

Table 1 illustrates survey measures for this study along with the frequency/timing of assessments.

Table 1: Measures	Assessment Month(s)
OUTCOMES	
Primary Outcome	
Size Appropriate Restraint Use (dichotomous)	6 and 12
Child Passenger Safety Score direct observation	6 and 12
Secondary Outcome	
Child Passenger Safety Score remote observation	ED/Baseline through 12
Exploratory Cost Measures	
Intervention Time (ED, Phone MI) for RA/Counselor	ED/Baseline and 2
Intervention Time (ED, Phone MI, texts, web app) for caregiver	ED/Baseline through 12
Material Costs - iPads, computers, maintenance	ED/Baseline through 12
Intervention Costs - Photograph review, texts, web app	ED/Baseline through 12
MODERATORS/MEDIATORS	
Caregiver Demographic Characteristics, reason for ED visit	ED/Baseline
Child Size	

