### 4.2 Total Number of Subjects and Sites

To test the Tiny Cargo, Big Deal Intervention, we anticipate the need to screen 10,000 caregivers to recruit 900 caregivers who will be enrolled in the study and randomized to intervention or control. All recruitment will occur in the Emergency Department (ED) at Lurie Children's Hospital of Chicago (LCH) or remotely via phone/email/text message. With this most recent IRB modification (3/26/21), we will also add recruitment via flyers in patient treatment rooms from Lurie Children's affiliate EDs (e.g., Central DuPage, Northwest Community) and Lurie Children's Immediate Care Centers (Lincoln Park and Northbrook).

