## Consent process:

After obtaining verbal consent, participants will self-administer a computerized screening assessment survey with validated measures assessing for further study eligibility. RAs will stay in the room while the participant takes the survey to be available to assist with patient questions during screening. Study RAs will utilize procedures from prior work to seamlessly integrate the ED-based assessment into the patient's ED stay to avoid interrupting their care.

For remote recruitment, the participant will record their consent to take the survey at the start of the survey after they have read the informational handout and will voluntarily complete the survey via their own personal device. The will take the survey in the privacy of their own home/location.

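### The planned net cost (TCBD minus control) cancels the cost of screening, so it understates the net cost of adopting a selective intervention in place of usual care

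*Combined protocol and SAP*

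**What the plan says.** The cost analysis is in section 6.1 (Exploratory Aim) and, more briefly, in section 2.2. It plans total costs, a cost per child, and a net cost. For the last, "Net costs (savings) will be calculated by subtracting mean costs per participant in the control condition" from the means for basic and enhanced TCBD. It also plans a cost-effectiveness figure in dollars per caregiver using a size-appropriate restraint correctly. Costs are taken from the participant and health-system perspectives, and the results are meant to guide uptake in EDs, doctors' offices and schools. Part of the stated motivation is that "preventive and screening recommendations can compete for implementation time from staff".

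The exploratory cost rows of Table 1 (section 3.3) are:
- "Intervention Time (ED, Phone MI) for RA/Counselor";
- caregiver time on the ED session, phone session, texts and web app;
- devices and their upkeep;
- photograph review, texts and web app.

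No row names screening. The resource components listed in section 6.1 do not name it either.

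Section 1.1 gives as the first feature of TCBD that it "targets caregivers with suboptimal child passenger safety behaviors", and section 2 calls the intervention selective. The control condition in section 3.1 is ordinary ED care with an information sheet. Section 4.2 says "we anticipate the need to screen 10,000 caregivers to recruit 900 caregivers who will be enrolled". For in-person screening, section 4.5 (Consent process) says "RAs will stay in the room while the participant takes the survey"; remote caregivers complete the survey on their own device.

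**The concern.** A site that adopts TCBD must first find the caregivers it is meant for. Screening is therefore part of what the site takes on, and a site that stays with usual care does not incur it. In the trial, both arms consist of people who have already been screened. A difference between the arms compares TCBD with a control group that carries the same screening history, which usual care in practice does not.

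The planned net cost answers one question: what does TCBD add once an at-risk caregiver has been identified? The stated purpose asks another: what does it cost to introduce the programme where nothing of the kind exists? For the second question the planned figure errs in one direction only, towards making TCBD look cheaper. A manager reading it as the price of adoption would leave out staff and caregiver time, although section 6.1 itself warns about unmeasured time costs.

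**Working it through.** **1. The plan's own counts.** The documents state no cost figure, so none can be reproduced. The sample counts agree: 0.80 × 900 = 720 = 204 + 516 (section 6.1). The recruitment yield in section 4.2 is 10,000/900 = 11.1 screens per enrolled caregiver.

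**2. The net-cost formula.** Let I and C be the mean costs per TCBD and control participant without screening, s the cost of one screen, and k the number of screens needed per caregiver found. Sections 3 and 5.1.1 place screening before enrolment and randomisation, so k × s is the same in both arms:

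(I + k × s) − (C + k × s) = I − C, for any k and s.

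Measuring screening and including it in both arms would not change the planned net cost.

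**3. The adoption contrast.** Against usual care without screening:

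(I + k × s) − C = (I − C) + k × s.

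The shortfall in the planned figure is k × s.

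**4. Range for k.**
- Upper guide: 11.1, from step 1. The 900 also had to agree to a randomised trial with 12 months of texts and photographs and to pass research exclusions, so an adopting site would not lose all of the same people.
- From the suboptimal-use prevalences in section 1.1, with k = 1/prevalence: toddlers, roughly 30%, 1/0.30 = 3.3; elementary school age, above 50%, at most 1/0.50 = 2; infants, about 10%, 1/0.10 = 10.
- Section 4.3 also admits caregivers who plan a premature transition. That raises the positive rate and lowers k.

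**5. Caregiver time.** Section 4.5 gives 5-10 minutes per screening survey.

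| Screens per caregiver found (k) | At 5 min | At 10 min |
|---|---|---|
| 2 (school age) | 10 min | 20 min |
| 3.3 (toddlers) | 17 min | 33 min |
| 10 (infants) | 50 min | 100 min |
| 11.1 (trial yield) | 56 min | 111 min |

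For toddlers and school-age children this is 10-33 caregiver-minutes per positive.

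**6. Staff time.** For in-person screens, staff minutes are at least of the same order, because the assistant stays in the room. For remote screens the caregiver completes the survey alone and staff time is small. The in-person/remote mix is not stated, although a note in section 4.3 says study tasks have gone fully remote.

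**7. Dollars.** The documents give no unit cost for s, so the shortfall can be given in minutes only.

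**The case against.** The strongest reply is that an arm difference is the standard incremental cost and is correct for caregivers already identified. That stands. The fault lies in using it as the cost of adoption.

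A second reply is that section 6.1 promises every relevant cost and names personnel, implementation and participant time, which could cover screening. It adds that Table 1 cannot be exhaustive, because it also omits the development and training costs that section 6.1 includes. This stands for the gross cost per child. A reader might infer that this figure too is understated, but the documents leave it open. The reply does not rescue the net cost, where screening cancels whether or not it is recorded.

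Three stronger readings also go beyond the documents:
- **About 11 screens per recipient as the programme's burden.** The 11.1 is a trial-recruitment yield, which includes refusals and research exclusions.
- **Screening as the largest time item.** Counselling (20 minutes), website demonstration (10) and expected phone counselling (20 × 0.75 × 0.5 = 7.5) make 37.5 minutes. Adding 56-111 minutes gives 2.5-4.0 times that base; adding 10-33 gives 1.3-1.9 times. Either way, the base leaves out text, web-app and photograph-review time that Table 1 counts, so no ranking follows.
- **The plan naming TCBD's own screen as a barrier.** The sentence on competing staff time is about preventive and screening recommendations in general.

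Finally, the aim is exploratory. That limits the weight of the point but does not answer it.

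**Conclusion.** The point holds for net cost. As defined, TCBD minus control cannot contain screening, so it understates the net cost of adopting a selective intervention against usual care. Dollars per caregiver using a size-appropriate restraint are understated in the same way if they are built on this net cost; the plan does not say which cost they use. For gross cost per child, the finding is only that inclusion of screening is unspecified.

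The size is uncertain. A reasonable working range is 10-33 caregiver-minutes per positive for toddlers and school-age children, more for infants, with the trial's 56-111 minutes as an upper guide. The lower range assumes that the prevalences in section 1.1 apply to the caregivers screened and that every positive caregiver takes up the programme. Staff time depends on the in-person/remote mix, and no dollar amount can be derived. Aims 1 and 2 are unaffected.

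**What to change.** In Table 1 and the Exploratory Aim of section 6.1, add a screening cost line: staff and caregiver minutes per completed screen, separately for in-person and remote screening, multiplied by the observed number of screens per screen-positive caregiver from the recruitment log. State whether gross cost per child includes it.

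Report net cost and cost-effectiveness twice:
1. as planned, labelled as the incremental cost among caregivers already screened;
2. with screening added to basic and enhanced TCBD only, against usual care without screening.

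Showing both avoids a dispute over scope. The screening logs and survey records are already planned, and staff minutes can be sampled, preferably while screening is under way because they are hard to recover later. The design does not change. The price is a little data collection and a less favourable cost figure.

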## 6.2 Statistical Methods

All subjects, once randomized, will be included in an intention-to-treat analysis and outcomes will be collected even if the caregiver does not engage in the randomly assigned intervention. We will evaluate randomization by testing for covariate (e.g. demographic characteristics) balance between initial treatment groups, and between the re-randomized treatment groups created after the 6-month follow-up. If significant differences are observed, we will adjust for these variables or conduct stratified analyses. All statistical hypothesis tests and power calculations will use a two-sided = 0.05.

**Aim 1:** To test the efficacy of the TCBD intervention compared to usual care for improving primary outcomes [i.e., size-appropriate restraint (dichotomous) and CPaSS (numeric)] at 12 months. We hypothesize greater proportions of children will be using a size-appropriate restraint and higher CPaSS among caregivers in the intervention groups (basic and enhanced) compared with the control group (usual care) at the 12-month assessment. **Statistical Analysis:** Our primary analytic tool for estimating treatment effects will be generalized linear models (GLMs), and for analyses involving joint analysis of multiple follow-up data points, we will use generalized linear mixed models (GLMMs), which allows direct modeling of the correlations between data points (e.g. repeated measurements on individuals), and the inclusion of individuals with incomplete data (e.g. missing time points). The GLM(M) framework also allows simple controlling for confounders (if necessary) through their inclusion in the model as covariates. For the analysis of binary outcomes, we will use logistic GLM(M)s and for numeric outcomes (CPaSS-D) we will initially specify linear (Gaussian) GLM(M)s; this choice will be scrutinized by analyzing model diagnostics. The primary inferential target will be the coefficient for the treatment group indicator, making this effectively equivalent to ANCOVA. Adjustment for the baseline measurement is important for guarding

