# Emergency Medicine Prospective Protocol

person (e.g., they move out of state), they may also send us photos of their child as they usually ride in their car via text message or via a video chat (e.g., Facetime or google hangout).

- **\*\*See section 9 of IRB app, "supporting documents" for a document called, "TCBD text library and error messages" and refer to the sheet labeled, "Response to errors."** This document provides scripted responses that the RA will use when major misuse and/or errors are visible during the Tiny Cargo check-ins. The TCBD intervention messages are referred to as "Scripted MI response" while the control group's responses are referred to as "scripted control response."
- After the 6-month follow-up assessment, caregivers in the intervention group only who continue suboptimal CRS use will be re-randomized to receive either the basic or enhanced intervention.
- The enhanced TCBD intervention group will include one additional motivational interviewing (MI) session by phone in Month 7/8 and one to two additional tailored text messages in Months 7-12 (total of 7 tailored tips during these months compared to 4 tailored tips for those in the basic TCBD). The extra text messages will be sent to those in the enhanced TCBD group until size-appropriate restraint use is observed. Caregivers receiving enhanced TCBD will be encouraged to obtain a free seat check with a certified child passenger safety technician (CPST) in the community.
- The basic TCBD intervention group will continue on in study without any changes.

**Study Phase:** Phone Counseling Session --Month 7/8

**Study Group:** Enhanced TCBD Intervention Group

**Setting:** In-person or remote

**Timing:** Within 1 month

Phone counseling session (enhanced TCBD intervention):

After the study subject completes their 6-month follow-up visit, the study team will determine if the child is using the recommended child restraint system (car seat or booster seat) for their age and size. The intervention group subjects whose children are NOT using the recommended restraint will be randomly assigned (like flipping a coin) to one of two groups. They cannot pick the group they will be in.

The groups are:

- Group 2 (basic TCBD): They will keep taking part in the study with the basic intervention and nothing will change.

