## 6 Statistical Plan

### 6.1 Sample Size and Power Determination

Briefly, our calculations are based on two-sample comparisons between groups (e.g., control and TCBD) using results from our pilot study that assessed percent size-appropriate child passenger safety behaviors at 6-month follow-up (referred to as the “response rate” below). For analyses involving multiple time points, these calculations represent a conservative lower bound on the power that would only be achieved if the effective sample equals 1 observation per person (i.e. perfect within-individual correlation). For the calculations below we assume: a) 17% response rate among controls; b) 25% response rate among TCBD caregivers at 6 Month (with 75% of TCBD caregivers re-randomized); and c) only 80% of the target sample (n=204 controls and n=516 TCBD in the initial dichotomy) will be available for analysis at follow-up. Components (a) and (b) are based on pilot data where the control group received generic educational materials and outcomes were assessed at 6-months. Component (c) is a conservative correction for attrition. For Aim 2, we estimated power while accounting for uncertainty in the group sizes by simulating response and re-randomization patterns according to the above probabilities and testing for significant between-group differences; this process was repeated 10,000 times and the power was estimated as the percent of replications in which a between-group difference was identified. Binary Outcome: For the binary response case, if the observed response rate is at least 29.4% among those receiving enhanced TCBD, it can be reliably (>80% power) distinguished from a control response rate of 17%. Analogously, a response rate of at least 27.6% among basic intervention would be reliably (>80% power) distinguished from control. Converted to Cohen's  $h$ , both differences reflect small-to-medium effect sizes ( $h = 0.30$  and  $h = 0.26$ , respectively). Numeric Outcome (CPaSS): If the standardized mean difference (i.e. Cohen's  $D$ ) is  $>0.25$  (a small-to-medium effect size), we can reliably distinguish between control and basic TCBD conditions. Similarly, if  $D \geq 0.28$ , a small-to-medium effect size, we will have sufficient power (80%) to distinguish the control and enhanced TCBD conditions. Aim 2: Monte Carlo studies of linear latent trajectory models indicate that a medium level of heterogeneity among the slopes and/or intercepts of the trajectories can be reliably recovered (power  $> 80\%$ ) with a total sample size of  $n=200$ , with power exceeding 95% when the level of heterogeneity is high; given that our sample size soundly exceeds 200, we expect sufficient ability to determine the underlying characteristic trajectory types. Nevertheless, we further justify our sample size with a brief simulation study. Assuming a final sample size of 720, conservatively assuming individuals are only measured at an average of 25% of the 12 monthly assessments, we simulate data from a population with four equally likely trajectory types: consistently low, consistently high, linearly decreasing, and starting high then dropping off. Because we have no basis for estimating variability in the score, we assumed mean/variance equivalence, consistent with the Poisson distribution. Due to the time required to fit such models, we only completed 200 simulation replications, where we were able to correctly conclude (based on BIC) that there were four

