**Aim 2:** To use latent growth curve models to identify characteristic trajectories for the CPaSS observed in digital photographs over the 12 study months and assess for correlates of the trajectory types. We hypothesize that caregivers will have different CPaSS trajectories in response to the basic intervention, the enhanced intervention, and the control condition. We expect to identify at least four patterns of response. **Statistical Analysis:** We will determine 12-month CPaSS trajectory types using adaptations of finite mixture models for the case where the units are trajectories. We will define trajectory shapes through methods combining semiparametric regression modeling (e.g., generalized additive models), with latent class regression, using the R package flexmix. Following convention, we will use the Bayesian Information Criteria (BIC) to determine the appropriate number of latent classes, while also making practical considerations to avoid overfitting, such as not allowing overly small groups to be created, as in previous applied work. Using the posterior probability of class membership, we place individuals into trajectory groups and treat that grouping as the outcome in a subsequent multinomial regression model to determine correlates of class membership, including treatment group, caregiver race/ethnicity, and child age group. If substantial uncertainty in class membership is found, outcomes in the multinomial model will be weighted accordingly.

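### Two unranked primary outcomes are each tested at two-sided 0.05, and the plan does not say whether one or both must succeed, or rank the Month 6 and basic/enhanced comparisons

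*Combined protocol and SAP*

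**What the plan says.** **Level and outcomes.** Section 6.2 sets the level once for everything: "All statistical hypothesis tests and power calculations will use a two-sided" 0.05 (the symbol before the figure is lost in the text). Aim 1 has a binary and a numeric primary outcome. Neither is ranked in sections 2, 2.1, 3.2, 3.3 (Table 1), 3.4.1 or 6.2. There is no testing order, alpha split or statement of what counts as success.

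**Contrast.** Section 6.2 says "The primary inferential target will be the coefficient for the treatment group indicator", which reads most naturally as TCBD versus control. The Aim 1 hypothesis, however, speaks of improvement "in the intervention groups (basic and enhanced) compared with the control group (usual care) at the 12-month assessment". Section 6.1 gives detectable effects only for the two versions separately. For restraint use, "a response rate of at least 27.6% among basic intervention would be reliably (>80% power) distinguished from control", with 29.4% for enhanced. For CPaSS the values are D = 0.25 for basic and 0.28 for enhanced, and of the latter it says "we will have sufficient power (80%) to distinguish the control and enhanced TCBD conditions". No power is stated for the pooled TCBD group. These figures follow a sentence beginning "For Aim 2, we estimated power while accounting for uncertainty in the group sizes by simulating response and re-randomization patterns", although they concern the Aim 1 outcomes. Aim 2 itself also expects "different CPaSS trajectories in response to the basic intervention, the enhanced intervention, and the control condition".

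**Who is in each version.** Section 3 says "caregivers in the intervention group only who continue suboptimal CRS use will be re-randomized to receive either the basic or enhanced intervention".

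**Time point.** Aim 1 in section 2 is set at 6 and 12 months. Sections 3.2 and 3.3 also list the primary outcomes at both months. Sections 2.1, 3.4.1 and 6.2 say 12 months.

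**The concern.** With two primary outcomes and a full 0.05 for each, the error attached to an overall efficacy claim depends on the success rule, and there is none. 'Either' and 'both' remain open until results are seen. Section 6.2 joins the outcomes with *and*, but as a statement of what is expected, not as a decision rule.

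The unsettled contrast adds a different risk. Enhanced holds only caregivers who had not responded at Month 6, while basic keeps every Month-6 responder. Neither is exchangeable with the full control group after Month 6, so an unweighted comparison would be biased unless Month-6 and Month-12 status were unrelated. Section 6.2 specifies no adjustment for this.

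**Working it through.** **Inputs.** Two-sided 0.05 and two primary outcomes (6.2). 204 control and 516 TCBD analysable, 17% control response, 75% of TCBD re-randomised (6.1), split 1:1 (3.2). The correlation between the two outcomes is not given. It is assumed to lie between 0 and 0.9. A positive value is plausible because the CPaSS scores mode selection (5.1.2).

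**1. The plan's own figures.** Enhanced n = 516 × 0.75 / 2 = 193.5. Basic n = 516 - 193.5 = 322.5.

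- Restraint use, pooled-variance z test, power = Φ[(|p2 - p1| - 1.96·SE0)/SE1]. For basic, 27.6% v 17%: SE0 = 0.0379, SE1 = 0.0362, so Φ(0.874) = 80.9%. For enhanced, 29.4% v 17%: 83.7% (80.5% with continuity correction).
- CPaSS, power = Φ[D/√(1/n1 + 1/n2) - 1.96]. For basic, 0.25/0.0895 - 1.96 = 0.83, giving 79.8%. For enhanced, 0.28/0.1003 - 1.96 = 0.83, giving 79.7%.

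The stated effects are therefore reproduced with an unadjusted 0.05 on each outcome. No multiplicity allowance is built into the sample size.

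**2. Two tests of one contrast, both nulls true** (bivariate normal test statistics, correlation ρ):

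- either significant, any direction: 1 - P(|Z1| < 1.96, |Z2| < 1.96); at ρ = 0 this is 1 - 0.95² = 0.0975
- either significant for benefit: 1 - P(Z1 < 1.96, Z2 < 1.96); at ρ = 0 this is 1 - 0.975² = 0.0494
- both significant: 0.05 + 0.05 - (either)

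| ρ (assumed) | Either, two-sided | Either, benefit only | Both |
|---|---|---|---|
| 0 | 9.75% | 4.94% | 0.25% |
| 0.3 | 9.51% | 4.76% | 0.49% |
| 0.5 | 9.07% | 4.54% | 0.93% |
| 0.7 | 8.35% | 4.17% | 1.65% |
| 0.9 | 7.04% | 3.52% | 2.96% |

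A single test has 5% two-sided and 2.5% for benefit. If both must succeed and only one null is true, error is at most 5%. Simulation with a 17% binary and a numeric outcome at 204 v 516 gave 10.0%, 9.7%, 9.1% and 8.4% for 'either' at correlations 0, 0.3, 0.5 and 0.65.

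**3. Selection in basic and enhanced.** Suppose TCBD has no effect and the true rate is 17% at both months. Let φ be the Month 6-12 correlation (assumed).

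- Month-6 non-responders: Month-12 rate = 0.17(1 - φ). This is the expected enhanced rate.
- Month-6 responders: Month-12 rate = 0.17 + 0.83φ.
- Basic is all responders (0.17) plus half the non-responders (0.415), in total 0.585 of TCBD. Expected rate = [0.17(0.17 + 0.83φ) + 0.415 × 0.17(1 - φ)]/0.585.

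| φ (assumed) | Basic | Enhanced | Control |
|---|---|---|---|
| 0.1 | 18.2% | 15.3% | 17% |
| 0.3 | 20.6% | 11.9% | 17% |
| 0.5 | 23.0% | 8.5% | 17% |

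At φ = 0.5 the basic figure is (0.0995 + 0.0353)/0.585 = 0.230. In simulation under the same null, the pooled TCBD test rejected 4.9-5.0% of the time, and weighted comparisons with control rejected 5.0-5.2% each.

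**4. Power of the pooled restraint-use test at 27.6% v 17%.** With 204/516 it is 86.5%. With 180/540, which is the 3:1 ratio of section 3.2 applied to 720, it is 83.4%.

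**The case against.** The strongest reply is that the plan nowhere says either outcome suffices. The hypothesis joins the two, and read as requiring both there is no inflation. That stands. A reader might infer that the trial runs at 8-10% error, but the documents support only the conditional figure. What they do show is that the rule is missing.

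A reader might also infer that an efficacy claim would carry more than 5% error. That does not follow. The hypothesis is directional, and false claims of benefit reach at most 4.9%. The 7-10% includes false findings of harm. The proper comparison for benefit is with 2.5%.

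Counting two outcomes by two versions of TCBD gives four tests and an apparent familywise error of about 15-17%. The documents do not support this as the primary error rate. Section 6.2 targets one treatment coefficient and does not commit to basic and enhanced as separate primary contrasts. Selection would in any case invalidate the calculation's premise of 5% per test. Nor does the plan commit to an unweighted comparison. It hypothesises and powers these contrasts and leaves the method open.

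Finally, the missing pooled power is a small gap. The pooled group has more participants than basic against the same controls, so the stated 27.6% is already a conservative bound.

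**Conclusion.** The concern holds as a missing decision rule. Two primary outcomes are each given the full two-sided 0.05 with no order, split or success criterion, and that does not depend on any assumption. The size does: if either outcome were allowed to carry the claim, two-sided familywise error at Month 12 would be about 7-10%, and false benefit claims about 3.5-4.9% instead of 2.5%, over assumed correlations of 0.9 to 0.

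The selection effect in basic and enhanced is a related gap. Its size rests on the assumed Month 6-12 correlation and on an unweighted analysis being used. The comparison of TCBD as initially randomised with control is free of it. The design is sound, and the plan should be amended before its confirmatory claim is tested.

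**What to change.** 1. In section 6.2, state TCBD as initially randomised versus control at Month 12 as the primary contrast. Test the two outcomes in a fixed order, each at two-sided 0.05, for example restraint use and then CPaSS.
2. Fix this rule before any Month-12 between-arm comparison is made. A bar on looking at any outcome by arm could not be met, because Month-6 restraint use in the TCBD arm determines re-randomisation.
3. Align Aim 1 in section 2, section 3.2 and Table 1 in section 3.3 with sections 2.1, 3.4.1 and 6.2, so that Month 6 is labelled secondary.
4. Make basic and enhanced versus control secondary, with an analysis that accounts for re-randomising Month-6 non-responders only, for example inverse-probability weighting.
5. In section 6.1, add the pooled test's power and clarify what the Aim 2 label on the simulation covers.

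**Cost.** Wording, one power statement and one specified secondary model; no extra participants. CPaSS cannot be claimed if restraint use fails, and basic and enhanced lose any primary status. The power of the first-ranked test is unchanged: about 83-86% for the pooled group at 27.6% v 17%. Requiring both outcomes would also settle the rule but costs more. With 80% power for each, both succeed in 64% of trials at correlation 0 (0.8 × 0.8) and 71% at 0.7.
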